	
An analysis of covariance (ANCOVA) model will be fit to the ranked values of the primary efficacy endpoint. The ANCOVA will have terms for ranked baseline seizure rate and randomized treatment group.
 
The primary Efficacy Analysis for Europe, Australia, New Zealand, and South Africa:
 
The primary efficacy analysis of the primary endpoint will be based on the MITT-M population.
 
The testing strategy for the primary efficacy endpoint (responder rate) is to compare each of the YKP3089 dosage groups with the placebo group. A step-down procedure will be used to ensure the type I error rate due to multiple treatment comparisons is controlled at the 5% level. Each of the YKP3089 dosage groups will be compared with the placebo group according to the following hierarchy:
 
1. 200-mg dosage group versus placebo group2. 400-mg dosage group versus placebo group3. 100-mg dosage group versus placebo group 
The 200-mg dosage group will be compared with the placebo group at a 2-sided 0.05 level as the first step. If no statistically significant difference is detected between the 200-mg dosage group and the placebo group, the procedure will stop and it will be concluded that none of the YKP3089 dosages are efficacious. If a statistically significant difference is detected between the 200-mg dosage group and the placebo group in favor of the 200-mg dosage group, the procedure will proceed to the next step to compare the 400-mg dosage group with the placebo group at a 2-sided 0.05 level. If a statistically significant difference is detected between the 400-mg dosage group and the placebo group in favor of the 400-mg dosage group, the procedure will proceed to the next step to compare the 100-mg dosage group with the placebo group at a 2-sided 0.05 level.
 
The data will be summarized using frequencies and percents of subjects achieving at least a 50% response to treatment, the responder rate. The responder data will be analyzed using a chi-square test.
 
Other Efficacy and Safety Analyses:
 
The percentage of subjects who have a 75%, 90% and 100% seizure reduction during the double blind period and the maintenance phase. Responder rates for partial seizure subtypes (including simple partial with motor component, complex partial, and secondarily generalized tonic-clonic seizures) will be summarized. Outcome measurements such as quality of life and clinical global impression change will be analyzed. Safety will be assessed by the frequency, severity, and timing of adverse events, as well as by clinical laboratory test values, 12-lead ECG recordings, vital sign measurements, physical and neurologic

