6.2 Study Endpoints

The primary efficacy endpoints reflect the United States Food and Drug Administration (FDA) recommendation of percent reduction in seizure frequency for registration which is adopted by many countries in the rest of the world, and the European Agency for the Evaluation of Medicinal Products (EMA) recommendation of the responder rate for registration in Europe, which is also adopted by Australia, New Zealand, and South Africa.

6.2.1 *Primary Efficacy Endpoint in the United States and the Rest of the World*

The primary efficacy endpoint to be evaluated for registration in the United States and the Rest of the World is the percent change from the pretreatment baseline phase in seizure frequency (average monthly seizure rate per 28 days) of all simple partial motor, complex partial, or secondarily generalized seizures compared with the double-blind treatment phase.

The baseline rate (B) is calculated by counting the number of seizures over the baseline period and dividing by the number of days in the interval with non-missing seizure data and then multiplying by 28. The double-blind rate (D) is calculated in a similar manner. The percent change is equal to $100 \times (D - B) / B$. Simple partial seizures without a motor/visual component will not be counted.

This value will be undefined if $B = 0$. For the primary efficacy analysis, there will not be any baseline values with zero seizures. However, for the analysis of seizure sub-types, there is a possibility that B may be zero. In this case, B will be set to a value of 1.

6.2.2 *Primary Efficacy Endpoint in the countries of Europe, Australia, New Zealand, and South Africa*

The primary efficacy endpoint to be evaluated for registration in the countries of Europe, Australia, New Zealand, and South Africa is the responder rate defined as a 50% or greater reduction during the maintenance phase of the double blind period in the seizure frequency from baseline.

The responder endpoint is a binary indicator endpoint defined as 1 if the primary endpoint is $\leq -50\%$, and 0 otherwise

6.2.3 *Secondary Efficacy Endpoint in the countries of Europe, Australia, New Zealand, and South Africa*

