The secondary efficacy endpoint to be evaluated for registration in the countries of Europe, Australia, New Zealand and South Africa is the percent change from the pretreatment baseline phase in seizure frequency (average monthly seizure rate per 28 days) of all simple partial motor, complex partial, or secondarily generalized seizures compared with the maintenance phase of the double-blind treatment phase.

The baseline rate (B) is calculated by counting the number of seizures over the baseline period and dividing by the number of days in the interval with non-missing seizure data and then multiplying by 28. The double-blind rate (D) is calculated in a similar manner. The percent change is equal to $100 \times (D-B)/B$. Simple partial seizures without a motor/visual component will not be counted.

This value will be undefined if $B=0$. For the primary efficacy analysis, there will not be any baseline values with zero seizures. However, for the analysis of seizure sub-types, there is a possibility that B may be zero. In this case, B will be set to a value of 1.

6.2.4 *Secondary Efficacy Endpoint in the United States and the Rest of the World*

The secondary efficacy endpoint to be evaluated for registration in the United States and the Rest of the World is the responder rate defined as a 50% or greater reduction during the double blind period in the seizure frequency from baseline. The responder endpoint is a binary indicator endpoint defined as 1 if the primary endpoint is $\leq -50\%$, and 0 otherwise

6.2.5 *Additional Secondary Efficacy Endpoints*

- Higher response rates of (defined by cutoffs of -75%, -90% and -100%) simple partial seizures with motor component plus complex partial seizures plus secondarily generalized tonic clonic seizures during the double-blind period and maintenance phase.

- Percentage change in other seizure types will be calculated in the same way as the primary endpoint except for selecting the specific seizure types:

- o Complex partial
- o Secondarily generalized tonic-clonic
- o Simple partial motor

6.2.6 ***Outcome Measurements***

6.2.6.1 *Clinical Global Impression of Change (CGIC)*

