7.3 Inclusion Criteria

Subjects must satisfy all of the following criteria to be enrolled in the study:

1. Male or female, age 18 to 70 years inclusive
2. Weight at least 40 kg
3. Written informed consent signed by the subject or legal guardian prior to entering the study in accordance with the ICH GCP guidelines. If the written informed consent is provided by the legal guardian because the subject is unable to do so, a written or verbal assent from the subject must also be obtained.
4. A diagnosis of partial epilepsy according to the International League Against Epilepsy's Classification of Epileptic Seizures. Diagnosis should have been established by clinical history and an electroencephalogram (EEG) that is consistent with localization related epilepsy; normal interictal EEGs will be allowed provided that the subject meets the other diagnosis criterion (ie, clinical history).

5. Have uncontrolled partial seizures despite having been treated with at least one AED within approximately the last 2 years.
6. During the 8-week baseline period, subjects must have at least 8 partial seizures including only simple partial seizures with motor component, complex partial seizures, or secondarily generalized seizures without a seizure-free interval of greater than 25 days any time during the 8 weeks baseline. Subjects must have at least 3 of these partial seizures during each of the two consecutive 4-week segments of the baseline period.
7. Currently on stable antiepileptic treatment regimen:
 - a) Subject must have been receiving stable doses of 1 to 3 AEDs for at least 4 weeks prior to screening (Visit 1) to be continued unchanged throughout the study
 - b) Vagal nerve stimulator (VNS) will not be counted as an AED; however, the parameters must remain stable for at least 4 weeks prior to baseline. The VNS must have been implanted at least 5 months prior to Visit 1.
 - c) Benzodiazepines taken at least once per week during the 1 month prior to Visit 1 for epilepsy, or for anxiety or sleep disorder, will be counted as 1 AED and must be continued unchanged throughout the study. Therefore only a maximum of 2 additional approved AEDs will be allowed. See Exclusion Criterion No. 12 for intermittent benzodiazepine rescue parameters.

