12 STATISTICAL METHODS AND PLANNED ANALYSES

12.1 Sample size estimation

A sample size of 100 subjects per treatment group will provide 80% power to detect a difference of 16% in median percent reduction in seizure frequency between an active dosage group and placebo group, at a 2-sided significance level of 0.05, assuming a standard deviation of 40%.

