12.3 Analysis Data Sets

For all populations, subjects will be analyzed according to the target (randomized) dosage group including subjects who fail to achieve the target dosage during the titration phase.

Enrolled subjects: All subjects who have given informed consent to participate in this study will be considered enrolled subjects.

Intention-to-treat (ITT): All randomized subjects will be considered intention-to-treat subjects.

Modified intention-to-treat (MITT) subjects: All randomized subjects who have taken at least one dose of YKP3089 (or placebo) and have any post-baseline seizure data will be considered modified intention-to-treat subjects.

Modified intention-to-treat (MITT-M) subjects in Maintenance phase: All randomized subjects who have completed the titration phase and have taken at least one dose of YKP3089 (or placebo) in the maintenance phase and have any maintenance phase seizure data will be considered modified intention-to-treat subjects in the maintenance phase.

Per protocol population (PP): All randomized subjects who have no major protocol violations and have at least 80% drug compliance will be considered per-protocol subjects.

Safety evaluable subjects (SE): All ITT subjects.

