12.6 Secondary Efficacy Analyses

12.6.1 *Secondary Efficacy Analysis in the countries of Europe, Australia, New Zealand, and South Africa*

The secondary efficacy analysis will be based on the MITT-M population.

The secondary efficacy analysis is to compare each of the YKP3089 dosage groups with the placebo group for the percent reduction in seizure frequency.

An analysis of covariance (ANCOVA) model will be fit to the ranked values of the change in seizure frequency during the maintenance phase. The ANCOVA will have terms for ranked baseline seizure rate and randomized treatment group. Ties will be handled using the default option in SAS.

It should be noted that the efficacy analysis uses a non-parametric approach. Because of this, effect sizes are not estimated and tested directly, since testing is made on the rank of the change

in seizure frequency. However, summary tables for the actual (not the ranked) change in seizure frequency will be presented.

12.6.2 *Secondary Efficacy Analysis in the United States and the Rest of the World*

The secondary efficacy analysis will be based on the MITT population

The secondary efficacy analysis is to compare each of the YKP3089 dosage groups with the placebo group for the responder rate.

The data will be summarized using frequencies and percents of subjects achieving at least a 50% response to treatment, the responder rate. The responder data will be analyzed using a chi-square test.

12.7 **Additional Secondary Efficacy Analyses**

These secondary efficacy analyses will be based on the MITT or MITT-M population

- Higher response rate of (75, 90 and 100%) of simple partial seizures with motor component plus complex partial seizures plus secondarily generalized tonic clonic seizures during the double-blind period and maintenance phase will be summarized.
- Median percent change for partial seizure subtypes (including simple partial with motor component, complex partial, and secondarily generalized tonic-clonic seizures) will be summarized.
- Seizure rate over time will be analyzed using following scheme
 - A moving average for each dose group will be computed using 4 week periods with 2 week overlap beginning from Visit 3 (V3-V5, V4-V6, V5-V6+2 weeks and so on)

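### Setting a zero subtype baseline to 1 scores a subject with no such seizures before or during treatment as a 100% reduction

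*Protocol*

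**What the plan says.** Protocol Section 6.2.1 defines the baseline rate B as the seizure count divided by the days with non-missing data, times 28. D is the same rate on treatment, and percent change is 100 × (D − B)/B. The section notes that B cannot be zero for the combined seizure types, but that for subtypes "there is a possibility that B may be zero. In this case, B will be set to a value of 1". Section 6.2.3 repeats the rule for the maintenance-phase endpoint.

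Section 6.2.5 carries the formula to complex partial, secondarily generalized and simple partial motor seizures: "Percentage change in other seizure types will be calculated in the same way as the primary endpoint except for selecting the specific seizure types". Section 12.7 then summarizes "Median percent change for partial seizure subtypes" and gives the population: "These secondary efficacy analyses will be based on the MITT or MITT-M population". Section 12.3 defines MITT as "All randomized subjects who have taken at least one dose of YKP3089 (or placebo) and have any post-baseline seizure data", with no requirement on any single subtype. The synopsis also lists "Responder rates for partial seizure subtypes" without a formula.

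Zero subtype baselines are to be expected. Inclusion criterion 6 sets its minimum on the three types together: "subjects must have at least 8 partial seizures including only simple partial seizures with motor component, complex partial seizures, or secondarily generalized seizures".

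**The concern.** The value 1 is not a neutral placeholder. It gives a subject with no seizures of a subtype an invented baseline of one per 28 days, and then credits the subject with losing it. Someone who never has secondarily generalized seizures receives the best possible score on that subtype, in whichever arm.

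The invented baseline also exceeds the smallest one that can be observed over 56 complete days, which is 0.5. A zero-baseline subject can therefore score better than a subject with one real baseline seizure and the same number on treatment.

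At stake is the meaning of the subtype tables. A reader of a subtype median takes it as change among people who have that seizure type. Under the rule it mixes real change with an imputation constant, in a proportion the table does not show.

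**Working it through.** **Inputs.** From Protocol Section 6.1: baseline 56 days, double-blind period 126 days, maintenance 84 days. From Sections 6.2.1 and 6.2.3: the formula and the rule. The plan gives no numerical result for this rule to reproduce. The planned "difference of 16% in median percent reduction in seizure frequency" (Section 12.1, SD 40, for combined types) is used below only to scale illustrations. It reproduces: 99 per group for 80% power, and 80.7% power with 100 per group.

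**Step 1: scores when B = 0 is set to 1.** With k seizures on treatment, D = 28k/126 or 28k/84, and the score is 100 × (D − 1).

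| k | 126 days | 84 days |
|---|---|---|
| 0 | −100% | −100% |
| 1 | −77.8% | −66.7% |
| 2 | −55.6% | −33.3% |
| 3 | −33.3% | 0% |
| 4 | −11.1% | +33.3% |
| 5 | +11.1% | +66.7% |

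**Step 2: ordering.** Take three seizures in 126 days, so D = 0.667. A baseline count of 0 (B set to 1) scores −33.3%. A count of 1 (B = 0.5) scores +33.3%. A count of 2 (B = 1.0) scores −33.3%, a tie. A count of 3 (B = 1.5) scores −55.6%. The ordering is wrong only against a single baseline seizure.

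**Step 3: how often this could occur.** Assume an unchanged Poisson rate r per 28 days. Then P(B = 0) = exp(−2r), and the on-treatment mean over 126 days is 4.5r. A zero-baseline subject scores as a 50% responder if k ≤ 2 and as an increase if k ≥ 5.

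| r | B = 0 | of these, 50% responders | of these, increases |
|---|---|---|---|
| 0.1 | 81.9% | 98.9% | 0.0% |
| 0.25 | 60.7% | 89.5% | 0.6% |
| 0.5 | 36.8% | 60.9% | 7.8% |
| 1.0 | 13.5% | 17.4% | 46.8% |
| 1.5 | 5.0% | 3.6% | 80.3% |

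For rarer subtypes the rule mostly manufactures responders. For more frequent ones, zero baselines are few and often score as increases.

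**Step 4: direction.** Subjects with none before and none during treatment can only move a median toward a larger reduction or leave it unchanged. Zero-baseline subjects with several new seizures pull the other way. Suppose 30% have B = 0, three quarters of them score above the median and the rest score −100%. With the other subjects normal (SD 40), the median becomes μ + 40 × Φ⁻¹((0.5 − 0.3 × 0.25)/0.7). Medians of −20 and −36 then become −9.1 and −25.1. If one half score above, there is no shift.

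**Step 5: arm differences.** Suppose instead that all zero-baseline subjects score −100% and form a share f of the arm. The median is μ + 40 × Φ⁻¹((0.5 − f)/(1 − f)). Equal shares below one half move both medians but keep the 16-point gap: at f = 0.3, −20/−36 becomes −42.6/−58.6. At f of one half or more, both medians are −100% and the gap is zero. With no drug effect (median −20 in both arms), shares of 0.3 and 0.4 give −42.6 and −58.7, a spurious gap of 16.1 points.

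**Step 6: simulation with all zero-baseline subjects kept.** Subject rates are gamma distributed and counts Poisson. The assumed on-treatment multipliers are 0.80 for placebo and 0.64 for active. Each scenario has 2,000,000 subjects. The entry minimum on combined types is not modelled. Medians over 126 days are shown as placebo/active.

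| Shape, mean per 28 days | B = 0 | With the rule (gap) | B > 0 only (gap) |
|---|---|---|---|
| 0.25, 2 | 49.2% | −77.8/−77.8 (0) | −27.3/−43.2 (15.9) |
| 0.5, 2 | 33.3% | −52.7/−55.6 (2.9) | −26.7/−43.2 (16.5) |
| 0.5, 4 | 24.2% | −33.3/−50.0 (16.7) | −23.2/−39.6 (16.3) |
| 0.5, 0.5 | 57.7% | −77.8/−100 (22.2) | −55.6/−55.6 (0) |
| 4, 4 | 1.2% | unchanged (15.8) | (15.8) |

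Over 20 scenarios (shapes 0.25 to 4, means 0.5 to 4), the gap under the rule, relative to B > 0 only, shrank by more than 1 point in 8, grew in 4 and stayed within 1 point in 8. No median moved toward a smaller reduction. If subtype responder rates use the same formula, their gap was never larger under the rule (7.0 against 12.5 points at shape 0.25, mean 2).

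**The case against.** The strongest reply is that little depends on this. Subtype medians are summarized without a test, carry no alpha and stand outside the testing hierarchy. The primary, main secondary and 75/90/100% response endpoints use combined types and cannot have a zero baseline. All of that is right, and it limits the reach.

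Second, the operative analysis plan has not been seen. The supplied SAP covers the open-label extension only (SAP Section 4), and SAP Section 6 refers to a separate double-blind SAP that may restrict the subtype tables. That stands as a limit on what can be said about the reported tables. It does not change the protocol's rule, which is stated twice.

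Third, the sizes rest on assumed rates and effects, and randomization balances zero-baseline shares in expectation. This is also fair. The simulation shows what can happen, not what will.

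Fourth, restricting to B > 0 is not a perfect benchmark. With sparse counts, medians move in coarse steps, and subjects selected for a baseline seizure regress to the mean. At mean 0.5 the B > 0 gap is zero for shapes 0.5 to 4, and at shape 0.5 both arms show −55.6% although the true placebo change is −20%. Three of the four scenarios in which the gap grew are of this kind. The direction is not universal either: with one common rate of 1.5 per 28 days, the rule gives −20.0 against −22.2 for placebo and −33.3 against −37.8 for active. These points weaken any claim about typical size. None touches the result in step 1, which needs no model.

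**Conclusion.** The concern holds. As written, the protocol scores a subject who never had a subtype as a complete success on that subtype, and scores up to four new seizures in 126 days (up to two in 84) as improvement. This follows from the stated formula alone.

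The effect on medians and arm differences depends on the share of zero-baseline subjects and their on-treatment counts, which the documents do not give. It ranges from nothing, where the subtype is common, to medians of −100% in both arms, where never-affected subjects are the majority. Arm gaps can shrink or grow. The synopsis responder rates are affected only if they use the same formula. The defect is confined to descriptive subtype summaries and should be fixed, subject to what the double-blind SAP says.

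**What to change.** Delete the sentence that sets B to 1 in Sections 6.2.1 and 6.2.3. For each subtype, limit percent change and responder rate to subjects with at least one baseline seizure of that subtype, and state n per arm. Report zero-baseline subjects separately, as the number and percent in each arm with any seizure of that subtype on treatment. State in Section 12.7 whether subtype responder rates are reported and by what formula, and align the double-blind SAP.

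The cost is one sentence in each of two sections, a short clarification in Section 12.7, a program filter, an n per arm in the subtype tables and one added descriptive table. No new data are needed and no alpha is involved. The price is smaller n. For rare subtypes, regression to the mean and coarse medians remain in every arm and can still obscure a difference, so those tables should be read with their n and baseline counts in view.

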6.4 Interim Analysis

No interim analysis will be performed

7 SELECTION OF STUDY POPULATION

7.1 Study Population and Sites

This trial will be sponsored by SK Life Science Inc in the United States and other countries. Approximately 520 subjects will be screened to achieve a minimum of 400 subjects randomly assigned to study drug, 100 subjects for each dose group: placebo or 100 mg, 200 mg, or 400 mg YKP3089.

7.2 Subject Recruitment

Subjects will be selected from the principal investigator's and Sub-investigator's existing patient population or may be referred by another physician. Sites may also advertise beyond their practice. All advertisements must be approved by the Sponsor and governing ethics committee. Subjects who have provided signed informed consent will need to complete the Screening visit assessments to confirm eligibility for the study.

7.3 Inclusion Criteria

Subjects must satisfy all of the following criteria to be enrolled in the study:

1. Male or female, age 18 to 70 years inclusive
2. Weight at least 40 kg
3. Written informed consent signed by the subject or legal guardian prior to entering the study in accordance with the ICH GCP guidelines. If the written informed consent is provided by the legal guardian because the subject is unable to do so, a written or verbal assent from the subject must also be obtained.
4. A diagnosis of partial epilepsy according to the International League Against Epilepsy's Classification of Epileptic Seizures. Diagnosis should have been established by clinical history and an electroencephalogram (EEG) that is consistent with localization related epilepsy; normal interictal EEGs will be allowed provided that the subject meets the other diagnosis criterion (ie, clinical history).

5. Have uncontrolled partial seizures despite having been treated with at least one AED within approximately the last 2 years.
6. During the 8-week baseline period, subjects must have at least 8 partial seizures including only simple partial seizures with motor component, complex partial seizures, or secondarily generalized seizures without a seizure-free interval of greater than 25 days any time during the 8 weeks baseline. Subjects must have at least 3 of these partial seizures during each of the two consecutive 4-week segments of the baseline period.
7. Currently on stable antiepileptic treatment regimen:
 - a) Subject must have been receiving stable doses of 1 to 3 AEDs for at least 4 weeks prior to screening (Visit 1) to be continued unchanged throughout the study
 - b) Vagal nerve stimulator (VNS) will not be counted as an AED; however, the parameters must remain stable for at least 4 weeks prior to baseline. The VNS must have been implanted at least 5 months prior to Visit 1.
 - c) Benzodiazepines taken at least once per week during the 1 month prior to Visit 1 for epilepsy, or for anxiety or sleep disorder, will be counted as 1 AED and must be continued unchanged throughout the study. Therefore only a maximum of 2 additional approved AEDs will be allowed. See Exclusion Criterion No. 12 for intermittent benzodiazepine rescue parameters.
8. Computed tomography (CT) or magnetic resonance imaging (MRI) scan performed within the past 10 years that ruled out a progressive cause of epilepsy. If a CT or MRI has not been performed within the past 10 years, one must be performed prior to randomization.
9. Ability to reach subject by telephone.
10. Use of an acceptable form of birth control by female subjects of childbearing potential (see Section 7.5).

Any potential exception to inclusion criteria allowing *de minimis* (clinically trivial and meaningless) variations must be approved by the medical monitor.

